#### **9.5.1.5 Peak expiratory flow rate**

All the patients are instructed to record PEF twice daily using an electronic Peak Flow Meter device, once in the morning and once approximately 12 hours later in the evening, from Run-in visit 101 and throughout the study.

PEF (liters/min) will be analyzed separately for morning and evening values. Mean values will be calculated over the 2 weeks Treatment Phase. Morning and evening PEF data averaged over the days of Run-in period will be used as baseline values.

Mean morning/evening PEF will be summarized by treatment. In addition, change from baseline in mean morning/evening PEF during the 2 weeks treatment will be summarized.

#### **9.5.1.6 Asthma symptoms based on e-Diary**

The e-Diary data on asthma symptoms will be summarized for:

- the mean daytime asthma symptom score
- the total daily symptom score
- percentage of days with no daytime symptoms
- percentage of nights with no nighttime awakenings
- percentage of mornings with no symptoms on rising
- percentage of asthma symptoms free days, i.e., days with no daytime symptoms and no nighttime awakenings and no mornings with symptoms on rising

Daily scores will be averaged for each patient over the days of the Run-in period (which will be used as the baseline value) and the 2 weeks treatment period. Days with no daytime symptoms, nights with no night-time awakenings, mornings with no symptoms on awakening, and days with no asthma symptoms will be expressed in percentage of days with data during the respective periods. The same periods as for average scores will be analyzed for percentage of days. For post-baseline periods only the days on double-blind treatment will be considered. In addition, summary statistics will be provided for changes from baseline.

### **9.5.2 Safety variables**

All safety parameters will be summarized on the safety set.

#### **Adverse events**

All treatment emergent AEs including asthma exacerbations will be summarized and listed. AEs starting on or after the time of the first inhalation of study drug but not later than 7 days (30 days in the case of a SAE) after the last inhalation will be classified as a treatment emergent AE. Any AEs that started during the study before the time of the first inhalation of study drug will be classified as a prior AE.

The following treatment emergent AE summaries will be produced, overall by system organ class and preferred term, overall by system organ class, preferred term and maximum severity, suspected drug-related AEs by system organ class and preferred term, SAEs by system organ class and preferred term, and AEs leading to permanent discontinuation of study-drug by system organ class and preferred term.

The number and percentage of patients with the most frequent AEs will be summarized by treatment.

In addition, AEs will be summarized by standardized MedDRA query (SMQ) level. The Compound Case Retrieval Strategy (CRS) will be used to determine the MedDRA search criteria to be used to identify AEs of special interest which will be summarized too.

### **Electrocardiogram (ECG) and vital signs**

Data from the electrocardiogram will be summarized by treatment and visit.

Vital signs (blood pressure and radial pulse rate) data will be summarized by treatment and visit.

The maximum (QTc, systolic blood pressure, pulse rate and heart rate) or minimum (diastolic blood pressure) post first dosing (i.e. post baseline) value will also be summarized. Changes from baseline will also be summarized by treatment.

Weight will be summarized by visit and treatment group. Changes from baseline will also be summarized by treatment. The baseline measurement will be the measurement at Visit 101.

All data will be included in the analysis regardless of rescue medication usage.

The number (%) of patients with treatment emergent pulse rate, systolic blood pressure and diastolic blood pressure outside the ranges of below defined notable values will be summarized by treatment group.

Notable values for vital signs and change from baseline will be summarized. A notable value is defined per age group as follows:

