### **Run-in epoch (Visit 101-Visit 199)**

Once patients' concurrent medications comply with the requirements of the study ([Section 5.5.6](#) and [5.5.8](#)) patients will enter a Run-in epoch.

The Run-in epoch is 2 weeks in duration (Visit 101 and 199) and will be used to further assess eligibility (including meeting reversibility and FEV1 criteria, collecting baseline patient characteristics, and reviewing fluticasone and rescue salbutamol/albuterol use).

Patients are instructed NOT to take their fluticasone inhaler in the morning of these study visits, and should bring it with them to the site. The patients should take their fluticasone inhaler at the beginning of each study visit, under supervision of the site staff. The patient will take their fluticasone inhaler back home with them and be instructed to take it as directed.

During Visit 101, study staff will administer the pediatric Asthma Control Questionnaire to the child. The Asthma Control Questionnaire – interviewer-administered (ACQ-IA) is further discussed in [Section 6.4.2](#).

Approximately two weeks after the start of the Run-in epoch (Visit 101 + 14 days), the patient will return to the clinic in the morning for Visit 199 (end of Run-in), to have all eligibility criteria reviewed along with their e-Diary and PEF meter and complete another ACQ-IA. If the patient continues to meet eligibility criteria (no salbutamol/albuterol taken within 6 hours of this visit and FEV1  $\geq 50\%$  and  $\leq 90\%$  of the predicted normal value for the patient) the patient will immediately continue to Visit 201 (Randomization/ Day 1).

If the patient's FEV1 and/or reversibility do not meet criteria at Visit 101, these assessments can be repeated one time, on a different day. For learning purposes, spirometry training can be provided prior to actual measurements.

[Table 6-1](#) displays all Run-in procedures.

For all subsequent study visits, the patient's parent(s)/legal guardian(s) should be instructed that their child does NOT take the morning dose of fluticasone, as they will take this dose at the site and the investigator will observe the inhalation technique of the child. Additionally, patients should NOT take any rescue salbutamol/albuterol for a minimum of 6 hours prior to arriving for their next study visit. If rescue medication is taken within 6 hours of a study visit, the visit must be rescheduled.

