### **Treatment epoch (Visit 201-Visit 299)**

If the patient continues to meet eligibility criteria, Visit 201 (randomization/ Day 1) occurs on the same day as Visit 199. Qualifying patients will be randomized to one of the two treatment groups below, with an equal (1:1) randomization ratio:

- Indacaterol acetate 75 µg delivered via Concept1 o.d. in the morning
- Indacaterol acetate 150 µg delivered via Concept1 o.d. in the morning

The treatment epoch will last 2 weeks. Patients will receive their first dose of study medication at the site, and the patient's parent/legal guardian should be instructed to give their child study medication at approximately the same time each day. Patients will return to the clinic 2 weeks later for the end of treatment visit (Visit 299).

All patients will be required to attend the clinic visits (Visit 201 and 299) where they will take their morning fluticasone dose, have pre-dose trough measurements of lung function prior to taking the study medication, and post-dose measurements.

Parents/legal guardian(s) will be instructed to record the time of their child's last dose of study medication taken the day prior (~Day 13) to their final treatment visit (Visit 299/Day 14). Additionally, parents/legal guardians should be instructed that their child should not take the last dose of study medication on the day of the last clinic visit (Visit 299/ end of treatment). Rather, the patient (parent/legal guardian) should bring their medication with them to the clinic and this dose will be administered under the supervision of study personnel. If study medication has not been taken in the morning on day 13 (last day before end of treatment Visit 299), the visit has to be rescheduled.

PK sampling (taken  $\leq$  2 hours pre-dose and at 15 minutes and 1 hour post-dose) will be performed at Visit 199/201 and 299 ([Table 6-1](#) through [6-3](#)). The ACQ-IA will also be done at Visit 299.

[figure not shown]
Patients should be seen for all visits on the designated day or as close as possible.

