#### **5.5.3.2 Handling of additional treatment**

The following non-study drug will be monitored as follows:

The non-study drug must be received by a designated person at the study site, handled and stored safely and properly, and kept in a secured location to which only the investigator and designees have access. Clinical supplies are to be dispensed only in accordance with the protocol.

The investigator must maintain an accurate record of the shipment and dispensing of the non-study drug in a drug accountability log. Monitoring of drug accountability will be performed by monitors during site visits or remotely and at the completion of the trial. Patients will be asked to return all unused non-study drug and packaging at the end of the Run-in for the Run-in medication and at the end of the study or at the time of discontinuation of study drug for the rescue medication.

These medications are:

- Salbutamol (100 µg) or albuterol (90 µg) used as rescue medication from Visit 1 to Visit 299
- Fluticasone propionate (100 µg b.i.d. or acceptable dose equivalent as outlined in [Section 3.1](#) used as Background medication from Visit 1 to Visit 299

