#### **6.5.3 Height and weight**

Height in centimeters (cm) and weight (to the nearest 0.1 kilogram [kg] in indoor clothing, but without shoes) will be measured at Visit 101, 199, and 299. BMI will be calculated based on height and weight.

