## 9.2 Patient demographics and other baseline characteristics

Demographic and baseline characteristics measured before randomization age, gender, race, ethnicity, height, weight, body mass index (BMI), relevant medical history, screening spirometric parameters (FEV1, FVC, FEV1/FVC), FEV1 reversibility, predicted and percentage of predicted FEV1, duration of asthma, history of asthma exacerbations, smoking exposure, prior concurrent medications (non-asthma and asthma-related), vital signs (systolic and diastolic blood pressure, pulse rate), peripheral blood eosinophil counts, QTc using Fridericia's correction and baseline ACQ-IA will be summarized by treatment group.

Continuous variables will be summarized using descriptive statistics (n, mean, 25th percentile, median, 75th percentile, standard deviation, minimum and maximum) and categorical variables will be summarized in terms of the number and percentage of patients in each category.

Baseline is defined as the last measurement before first dose of study drug.

No statistical analyses will be provided for baseline comparability among the treatment groups.

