## **9.7 Sample size calculation**

The sample size of 72 patients evaluable for the primary endpoint in the study is based on pragmatic considerations and per agreement with EU Pediatric Committee (PDCO), not based on statistical considerations. It is assumed that approximately 10% of patients will not complete the trial so that 80 patients need to be randomized to ensure 72 patients will be evaluable for the primary endpoint.

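### Section 9.5.2 takes the weight baseline from Visit 101, although Section 9.2 points to the pre-dose weight at Visit 199, so the reported weight change spans the run-in as well as treatment.

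*Protocol*

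**What the plan says.** Section 9.5.2 (Electrocardiogram and vital signs) plans a summary of weight by visit and treatment group, and of changes from baseline by treatment. It then fixes the starting point: "The baseline measurement will be the measurement at Visit 101".

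Section 9.2 lists weight among the baseline characteristics to be tabulated and gives one rule for all of them: "Baseline is defined as the last measurement before first dose of study drug".

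Section 6.5.3 says height and weight "will be measured at Visit 101, 199, and 299", and Table 6-1 marks the same three visits, at Days -14, 1 and 14. Table 6-1 shows no weight at Visit 201. Section 3.1 places the first dose at Visit 201 and states that "Visit 201 (randomization/ Day 1) occurs on the same day as Visit 199". The Visit 199 weight is therefore the last one before dosing.

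**The concern.** One variable has two baselines. Under Section 9.2 the baseline table shows the Visit 199 weight. Under Section 9.5.2 the change table starts from Visit 101, two weeks earlier. A reader who adds the reported mean change to the reported baseline mean will not, in general, arrive at the Visit 299 mean.

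The second consequence is interpretive. A safety table of change from baseline by treatment is normally read as change since treatment began. Here it would also contain whatever happened to the child's weight during the run-in, before any indacaterol. There is no placebo arm (Section 3.2), so nothing in the design removes that component from either dose's own change. In children aged 6 to 11, who are growing, some weight gain over the run-in is to be expected.

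Section 9.5.2 does not use this starting point consistently. For the extreme post-dose ECG and vital-sign values, the same subsection treats the time after first dosing as the post-baseline period. On a Visit 101 baseline, the pre-dose weight at Visit 199 would itself count as post-baseline.

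**Working it through.** The protocol gives no figure for weight change, so there is none to reproduce. The check has three steps: which visit each section makes the baseline, how long the resulting interval is, and how far a share of time can be read as a share of weight.

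**Step 1. Which visit is the baseline?**

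| Source | Rule | Baseline weight |
|---|---|---|
| Section 9.2, with Section 6.5.3 and Table 6-1 | Final value before dosing; weights at Visits 101, 199, 299 | Visit 199, Day 1 |
| Section 9.5.2 | Visit named explicitly | Visit 101, Day -14 |

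The two rules select different measurements whenever the Visit 199 weight exists, and it is scheduled for every patient who reaches randomization.

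**Step 2. How much of the interval precedes indacaterol?**

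Inputs: a two-week run-in between Visits 101 and 199, with Visit 199 set at Visit 101 plus 14 days (Section 3.1, Run-in epoch); "The treatment epoch will last 2 weeks" (Section 3.1, Treatment epoch); and the days in Table 6-1.

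Formula: pre-dose share = (Visit 199 - Visit 101) / (Visit 299 - Visit 101).

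- 14-day run-in, then Day 1 to Day 14: 14 / (14 + 13) = 14/27 = 52%.
- Nominal two weeks plus two weeks: 14 / (14 + 14) = 14/28 = 50%.
- Table days with a Day 0 counted: 15 / (15 + 13) = 15/28 = 54%.

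Visit 299 also serves as the early discontinuation visit and includes a weight. For those patients the share is larger: 14 / (14 + 9) = 61% at Day 10, and 14 / (14 + 6) = 70% at Day 7.

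With Visit 199 as baseline the interval is 13 days and the pre-dose share is 0%.

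**Step 3. From time to kilograms.**

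Let k be the rate of weight change during treatment divided by the rate during run-in. The run-in share of the weight change is 14 / (14 + 13k).

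- k = 1: 14/27 = 52%.
- k = 0.5: 14/20.5 = 68%.
- k = 2: 14/40 = 35%.

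The share of time equals the share of weight only at k = 1, and the protocol gives no basis for choosing k.

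For absolute scale, assume steady growth of 2 to 4 kg per year. This range is an assumption and is not in the protocol.

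| Growth assumed | 14 run-in days | 13 treatment days | 27 days |
|---|---|---|---|
| 2 kg/year | 0.08 kg | 0.07 kg | 0.15 kg |
| 3 kg/year | 0.12 kg | 0.11 kg | 0.22 kg |
| 4 kg/year | 0.15 kg | 0.14 kg | 0.30 kg |

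Each entry is the annual rate times days/365. Under this assumption the Visit 101 baseline adds about 0.08 to 0.15 kg to each arm's mean change with no drug effect. Weight is recorded to 0.1 kg in indoor clothing (Section 6.5.3), so the addition is close to the resolution of the measurement.

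**The case against.** The strongest reply is that a specific rule overrides a general one. The Section 9.2 definition stands in the section on demographics and baseline characteristics. The protocol sets variable-specific baselines elsewhere: a run-in average for peak flow (Section 9.5.1.5) and symptom scores (Section 9.5.1.6), and the mean of two pre-dose values for FEV1 (Section 6.5.6). An analyst reading the weight paragraph knows what to do. This stands as far as it goes: it settles which rule would be programmed. It does not explain why a pre-dose weight already in hand is passed over. The peak flow and symptom baselines average daily diary data, and the FEV1 baseline is taken on Day 1, so none is a precedent for using the earlier of two clinic measurements. Safety laboratory samples are drawn at the same three visits (Section 6.5.4), and Section 9.5.2 sets no Visit 101 exception for them.

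A second reply is that weight is also summarized by visit, so the Visit 199 mean will appear for each arm and the mean run-in change can be read off approximately. This also stands and lowers the stakes. It is only a partial remedy: the spread of the change since Visit 199 cannot be recovered from by-visit means, and the means may rest on different children at different visits.

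Third, no decision depends on the table. Weight is not named in the safety objective (Section 2.2), has no notable-value criterion in Section 9.5.2, and is not tested. This stands.

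Three stronger readings are tempting, and the protocol does not support them:

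- A reader might infer that the dose comparison is biased. Randomization follows the run-in, so pre-treatment change is expected to be the same in both arms.
- A reader might infer that the run-in change reflects washout and the switch to fluticasone. Washout must be complete before Visit 101 (Section 3.1, Table 5-1). Fluticasone is "used as Background medication from Visit 1 to Visit 299" (Section 5.5.3.2), so the switch falls in the run-in only for children whose Visits 1 and 101 coincide.
- A reader might infer that the protocol calls the figure an on-treatment or drug-related change. It says only change from baseline, by treatment.

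**Conclusion.** The inconsistency is real. Section 9.5.2 names Visit 101 as the weight baseline, while Section 9.2 together with the visit schedule gives Visit 199. As written, the change at Visit 299 covers about 27 days, about 14 of them before any indacaterol. This mixes pre-treatment change into each arm's within-arm figure and separates the change table from the baseline table.

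The 50-54% is a share of time for patients who complete treatment on schedule. A reader might infer that half of the weight change itself comes from the run-in. That would require weight to change at the same rate in both epochs; with rates differing twofold in either direction the share ranges from 35% to 68%. Nor does pre-indacaterol mean untreated, since background fluticasone is taken throughout.

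The severity is the lowest: one descriptive safety summary over two weeks, with no effect on the primary endpoint and no bias between doses. The conclusion rests on the protocol text alone and assumes that the Visit 199 weight is collected as scheduled.

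**What to change.** In Section 9.5.2, replace the sentence naming Visit 101 with a statement that baseline weight is the last pre-dose measurement, namely the Visit 199 value, and that the Visit 101 value is used only if Visit 199 is missing. If the earlier weight is of interest, show the Visit 101 to Visit 199 change as a separate line labelled as run-in change. If Visit 101 was chosen on purpose, Section 9.5.2 should give the reason and the table should state the interval it covers.

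The cost is one sentence in the protocol or SAP. The Visit 199 weight is already on the schedule, so no visit, procedure or data item is added.

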#### **Systolic blood pressure:**

“Low” criterion:  $\leq 80$  mmHg (6-8 years) or  $\leq 85$  mmHg (9-11 years) and decrease from baseline  $\geq 20$  mmHg ([Haque et al 2007](#))

“High” criterion:  $\geq 115$  mmHg (6-8 years) or  $\geq 120$  mmHg (9-11 years) and increase from baseline  $\geq 20$  mmHg ([Fourth Report 2004](#))

#### **Diastolic blood pressure:**

“Low” criterion:  $\leq 40$  mmHg (6-8 years) or  $\leq 45$  mmHg (9-11 years) and decrease from baseline  $\geq 20$  mmHg ([Horan et al 1987](#))

“High” criterion:  $\geq 75$  mmHg (6-8 years) or  $\geq 80$  mmHg (9-11 years) and increase from baseline  $\geq 20$  mmHg ([Fourth Report 2004](#))

#### **Pulse rate:**

“Low” criterion: decrease from baseline  $\geq 25\%$  to a value  $< 70$  bpm (6-8 years) or  $< 60$  bpm (9-11 years)

“High” criterion: increase from baseline  $\geq 25\%$  to a value  $> 115$  bpm (6-8 years) or  $> 110$  bpm (9-11 years) (according to internal draft ECQ\_QT Guidelines)

Categorical QTc values and changes from baseline will be summarized as the number (%) of patients with new (treatment-emergent) QTc  $>450$ ,  $>480$  and  $>500$  ms.

QTc change from baseline will be presented as QTc changes, both positive and negative, or 0-30 ms,  $>30$  ms, and  $>60$  ms.

Notable QT values are defined as QTc increases of  $>30$  and  $>60$  ms, and QTc  $>500$  ms.

QTc will be calculated from the QT interval and RR (in seconds) using the Fridericia formula or dependent on the age Bazett formula, respectively.

Vital signs and ECG data measured more than 7 days after last inhalation of study drug is regarded as post-treatment data and will not be summarized, only listed.

### **Laboratory data**

The laboratory parameters (hematology, blood chemistry including glucose and potassium, urinalysis and evening plasma cortisol, eosinophil counts) will be summarized by treatment, visit and time point, including changes from baseline.

All laboratory data will be listed with abnormal values flagged. The laboratory values and the change from baseline for continuous laboratory parameters will be summarized at each visit.

A frequency table of results for categorical laboratory parameters will be produced by visit.

Shift tables relative to the normal reference ranges will be used to summarize the change from baseline to post-baseline by visit for each laboratory parameter.

The number and percentage of patients with newly occurring or worsening laboratory abnormalities meeting the clinically notable criteria will be summarized by laboratory parameter, scheduled post-baseline visit and time point and additionally at any time on treatment considering all post-baseline data from scheduled, unscheduled and premature discontinuation visits. Similar analysis will be done for newly occurring or worsening abnormalities in liver function tests (LFT).

Laboratory data measured more than 7 days after last inhalation of study drug is regarded as post-treatment data and will not be summarized, only listed.

### **9.5.3 Pharmacokinetics**

For PK concentration data, listings and descriptive statistics will be provided. The descriptive statistics will comprise arithmetic and geometric means, SD, median, minimum and maximum for plasma indacaterol concentrations at pre-dose ( $<2$  hours) and at 15 min and 1 hour post-dose at Visit 199/201 and 299. Plasma concentrations will be expressed in pg/mL units. All concentrations below the lower limit of quantification or missing data will be labeled as such in the concentration data listings. Concentrations below the lower limit of quantification will be treated as zero in summary statistics of concentration data. In addition, the plasma concentration data from this study may be combined with data from other studies to perform a population PK analysis, which will follow the principles outlined in the FDA Guidance for Industry 1999.

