### 2.2 Secondary objective(s)

- To evaluate the systemic exposure to indacaterol in plasma following sparse pharmacokinetic (PK) sampling on Day 1 and Day 14 after oral inhalation of indacaterol acetate 75 µg and 150 µg
- To evaluate the clinical effects and pharmacodynamics of indacaterol acetate (75 µg and 150 µg o.d.) after 2 weeks of treatment in terms of:
  - Pediatric interviewer-administered Asthma Control Questionnaire (ACQ-IA) score at Week 2
  - FEV1 and forced vital capacity (FVC) rate at 30 minutes and 1-hour post dose at Week 2
  - Rescue medication usage over 2 weeks of treatment as determined by patient diary data
  - Symptoms as recorded by patient e-diary
  - Pre-dose morning and evening peak expiratory flow (PEF) over 2 weeks of treatment as determined by electronic peak flow meter data.
- To evaluate the safety (including labs, vital signs, ECG, adverse events), and tolerability of indacaterol acetate (75 and 150 µg o.d.) over 2 weeks of treatment.

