**Figure 3-1 Study design**

### 3.2 Rationale for study design

This study is a randomized, double-blind, parallel-group study, with a 2-week treatment duration to assess 2 different doses of indacaterol acetate. The primary endpoint, trough FEV1, will be evaluated as change from baseline (randomization) after 2 weeks. This is considered an adequate duration to demonstrate improvements in the primary endpoint of lung function based on the known pharmacodynamic properties of indacaterol.

In order to preserve the integrity of the study, a randomized, double-blind study design is used. This design enables the study treatments to be given for an appropriate and practical length of time to assess the efficacy and safety of the treatments. The study design does not include a placebo control, as this would not be considered ethical in this population of pediatric asthma patients with GINA  $\geq$  Steps 2 and 3 (GINA 2015).

The primary objective of this trial is to evaluate the efficacy of 2 doses of indacaterol in patients with persistent asthma in terms of lung function (measured by pre-dose FEV1). Other efficacy endpoints include peak expiratory flow, rescue medication, and FEV1 at 30 minutes and 1 hour post-dose.

Additional secondary endpoints include the evaluation of the systemic exposure to indacaterol in plasma according to a sparse PK sampling ( $\leq$  2 hours pre-dose, and 15 minutes and 1 hour post-dose). This will allow comparison of the systemic exposure to indacaterol after single dose (Day 1) and at steady state (Day 14) observed in these pediatric patients with that collected in adult healthy subjects or patients (historical data). Safety is also evaluated.

The lung function data combined with systemic exposure will be used to identify an appropriate dose of indacaterol which will be carried forward to the Phase 3 pediatric trials. The primary endpoint, change in baseline of pre-dose trough FEV1, will be evaluated descriptively as a function of change from baseline between the two indacaterol doses. Taken together with systemic exposure for each dose, which will be compared with historical PK data collected in adults, an appropriate dose will be selected.

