### **3.4 Rationale for choice of comparator**

It was considered appropriate to explore two doses of indacaterol acetate, 75 µg o.d. and 150 µg o.d. in 6-11-year-olds and to compare the systemic exposure obtained in this trial with that obtained in adults (historical data). Relative differences in lung function between 2 doses will be evaluated descriptively.

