## **5.4 Treatment blinding**

Patients, investigator staff, persons performing the assessments, and data analysts will remain blind to the identity of the treatment from the time of randomization until database lock, using the following methods:

- Randomization data are kept strictly confidential until the time of unblinding, and will not be accessible by anyone involved in the study
- The identity of the treatment will be concealed by the use of study drugs that are all identical in packaging, labeling, and schedule of administration, appearance, taste, and odor.

The randomization codes associated with patients/subjects from whom PK samples are taken will be disclosed to PK bioanalysts who will keep PK results confidential until data base lock.

Unblinding will only occur in the case of patient emergencies (see [Section 5.5.9](#)) and at the conclusion of the study.

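### Section 9.5.3 asks for geometric means of indacaterol concentrations but sets every value below the quantification limit to zero, so one such value makes a cell's geometric mean zero or undefined

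*Protocol*

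**What the plan says.** Section 9.5.3 of the protocol sets out the summaries of the concentration data: "The descriptive statistics will comprise arithmetic and geometric means, SD, median, minimum and maximum for plasma indacaterol concentrations at pre-dose", and likewise at 15 minutes and 1 hour after dosing, at Visits 199/201 and 299. Later in the same paragraph it fixes the rule for values below the lower limit of quantification (LLOQ): "Concentrations below the lower limit of quantification will be treated as zero in summary statistics of concentration data". The labelling of BLQ and missing values that it also describes applies to the data listings, not to the summaries. No other section gives a separate rule for the geometric mean.

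These summaries serve a secondary objective in section 2.2: "To evaluate the systemic exposure to indacaterol in plasma following sparse pharmacokinetic (PK) sampling on Day 1 and Day 14". Section 3.2 also gives them a part in choosing the Phase III dose: "Taken together with systemic exposure for each dose, which will be compared with historical PK data collected in adults, an appropriate dose will be selected".

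**The concern.** A geometric mean exists only for positive values. The plan asks for one and then puts zeros into the data from which it is computed. This is not a detail left for the statistical analysis plan. The protocol states a rule for all summary statistics, and that rule defeats one of the statistics it requires. An analysis plan that followed the protocol would inherit the fault, and one that used another rule would depart from the protocol.

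What is at stake is one of six descriptive statistics. Because section 9.4.2 rules out inferential testing and bases dose selection on the totality of the data, descriptive tables carry the exposure evidence, so each required entry should be computable. If the gap were noticed only after unblinding, the substitute rule would be chosen with the results in view.

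**Working it through.** **Inputs from the protocol**
- Two doses, randomized 1:1 (sections 3.1 and 5.2).
- Three sampling times (pre-dose, 15 minutes, 1 hour) on two days (sections 3.1 and 6.6.1), in all patients.
- 80 randomized and 72 evaluable (section 9.7). The 72 refers to the FEV1 endpoint. The protocol gives no PK-evaluable number, so 36 per arm is an assumption here; 40 per arm is the full randomized number.
- No LLOQ and no BLQ rate are stated. All rates below are assumptions.

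**Step 1: the algebra.** GM = (x₁ · x₂ · … · xₙ)^(1/n) = exp(mean of ln xᵢ). If any xᵢ = 0, the product is 0 and ln 0 does not exist. The result is 0 or undefined, whatever the other n − 1 values are.

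Illustration with simulated data (36 log-normal values, true median 100 pg/mL, log-SD 0.5), with the lowest value treated as BLQ and set to zero:

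| Statistic (pg/mL) | No BLQ value | One BLQ value set to 0 |
|---|---|---|
| Geometric mean | 102.8 | 0 |
| Arithmetic mean | 114.1 | 113.4 |
| Median | 106.6 | 106.6 |

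In general, setting one BLQ value among 36 to zero lowers the arithmetic mean by at most LLOQ/36.

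**Step 2: the cells.** 2 doses × 2 days × 3 times = 12 cells. Two of them, Visit 199 pre-dose in each arm, precede the first dose of study drug. Table 5-1 also stops once-daily long-acting beta-agonists at least 14 days before Visit 101, and a run-in of about 14 days follows, giving roughly 14 + 14 = 28 days. These two cells should be almost entirely BLQ. The remaining 12 − 2 = 10 cells depend on the BLQ rate.

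**Step 3: the chance that a cell fails.** With BLQ rate q, the same for each child and independent between children, P(at least one BLQ) = 1 − (1 − q)ⁿ.

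| Assumed q | n = 36 | n = 40 |
|---|---|---|
| 0.5% | 17% | 18% |
| 1% | 30% | 33% |
| 2% | 52% | 55% |
| 5% | 84% | 87% |
| 10% | 98% | 99% |

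Failure becomes more likely than not at q = 1 − 0.5^(1/n), which is 1.9% for n = 36 and 1.7% for n = 40.

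**Step 4: the bias of an LLOQ/2 rule.** Assume log-normal concentrations with σ = √ln(1 + CV²), let z be the standard normal quantile of q and φ the normal density. The relative bias of the geometric mean is exp{q(σz − ln 2) + σφ(z)} − 1.

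| CV | q = 1% | q = 2% | q = 5% | q = 10% |
|---|---|---|---|---|
| 40% | −0.56% | −1.10% | −2.63% | −4.98% |
| 60% | −0.50% | −0.97% | −2.28% | −4.21% |
| 100% | −0.41% | −0.77% | −1.71% | −2.95% |

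Substitution at LLOQ/2 thus costs at most about 5% over this range, where the zero rule loses the statistic altogether.

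**The case against.** The strongest reply is that no consequence has been shown. The only cells certain to fail come before any study drug, where a geometric mean tells the reader nothing. For the other ten, the probabilities rest on assumed BLQ rates; if nearly all samples after the first dose are quantifiable, nothing happens. No named decision rests on the geometric mean either: sections 3.2 and 3.4 name no metric for the comparison with adults, and the optional population PK analysis would not use these tables. A zero or blank entry also reveals itself. Finally, a narrow exception could be set in the analysis plan before lock without bias, since section 5.4 says the randomization codes "will be disclosed to PK bioanalysts who will keep PK results confidential until data base lock".

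Most of this stands as a limit on importance. The probabilities show how few BLQ values it takes to lose a cell; they do not forecast this trial, and no bias in the adult comparison is claimed. But none of it removes the conflict: the protocol fixes the zero rule itself, without exception, in the paragraph that requires the geometric mean. That the gap can be closed before lock is a reason to close it.

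**Conclusion.** The concern holds, as a minor point. As written, section 9.5.3 cannot deliver a usable geometric mean in any cell that contains a BLQ value. That follows from the text and needs no assumption. Two of the 12 cells are practically certain to be affected, harmlessly. In each of the other ten, the chance of failure runs from 17% at a 0.5% BLQ rate to 98% at 10% with 36 children per arm. Those figures assume the BLQ rate, the number of PK-evaluable children, and independence between children. Confidence is high for the conflict in the text, and does not extend to how often it will occur. The arithmetic mean, SD, median, minimum and maximum remain computable, and the primary endpoint is unaffected.

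**What to change.** Amend section 9.5.3 as follows:

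- Limit the zero rule to the arithmetic mean, SD, median, minimum and maximum.
- Fix one non-zero rule for the geometric mean before database lock and unblinding. LLOQ/2 is simple; a left-censored log-normal estimate is less biased but adds a distributional assumption.
- Report the number BLQ out of N in every cell.
- Show the geometric mean as not calculable at Visit 199 pre-dose and wherever more than half the values are BLQ.

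The cost is a short amendment to one section and minor programming. With LLOQ/2 there is the small downward bias shown in the working, and a row may show a minimum of 0 beside a positive geometric mean, so a footnote should state both rules.
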